| 
Grade 1 No dose modification
 | 
Symptomatic and topical therapy should be considered for low-grade (Grade 1 or 2, unless otherwise specified) events.
 |
| 
Grade 2 Hold study drug/study regimen dose until Grade 2 resolution to Grade ≤1.
 
If toxicity worsens, then treat as Grade 3 or Grade 4.
 
Study drug/study regimen can be resumed once event stabilizes to Grade ≤1 after completion of steroid taper.
 
Patients with endocrinopathies who may require prolonged or continued steroid replacement can be retreated with study drug/study regimen on the following conditions:
 
 1. The event stabilizes and is controlled. 2. The patient is clinically stable as per Investigator or treating physician's clinical judgement. 3. Doses of prednisone are at ≤10 mg/day or equivalent. | 
For persistent (>3 to 5 days) low-grade (Grade 2) or severe (Grade ≥3) events, promptly start prednisone 1 to 2 mg/kg/day PO or IV equivalent. Some events with high likelihood for morbidity and/or mortality – e.g., myocarditis, or other similar events even if they are not currently noted in the guidelines – should progress rapidly to high dose IV corticosteroids (methylprednisolone at 2 to 4 mg/kg/day) even if the event is Grade 2, and if clinical suspicion is high and/or there has been clinical confirmation. Consider, as necessary, discussing with the study physician, and promptly pursue specialist consultation.
 |
| 
Grade 3 Depending on the individual toxicity, study drug/study regimen may be permanently discontinued. Please refer to guidelines below.
 | 
If symptoms recur or worsen during corticosteroid tapering (28 days of taper), increase the corticosteroid dose (prednisone dose [e.g., up to 2 to 4 mg/kg/day PO or IV equivalent]) until stabilization or improvement of symptoms, then resume corticosteroid tapering at a slower rate (>28 days of taper).
 
More potent immunosuppressives such as TNF inhibitors (e.g., infliximab) (also refer to the individual sections of the imAEs for specific type of immunosuppressive) should be considered for events not responding to systemic steroids. Progression to use of more potent immunosuppressives should proceed more rapidly in events with high likelihood for morbidity and/or mortality – e.g., myocarditis, or other similar events even if they are
 |
| 
Grade 4 Permanently discontinue study drug/study regimen.
 | |

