Dosing Modification and Toxicity Management Guidelines for Immune-Mediated, Infusion-Related, and Non-Immune-Mediated Reactions (MEDI4736 Monotherapy or Combination Therapy With Tremelimumab or Tremelimumab Monotherapy) 1 November 2017 Version

General Considerations

| Dose Modifications | Toxicity Management |
|---|--|
| 
Note: For Grade ≥ 3 asymptomatic amylase or lipase levels, hold study drug/study regimen, and if complete work up shows no evidence of pancreatitis, study drug/study regimen may be continued or resumed.
 
Note: Study drug/study regimen should be permanently discontinued in Grade 3 events with high likelihood for morbidity and/or mortality – e.g., myocarditis, or other similar events even if they are not currently noted in the guidelines. Similarly, consider whether study drug/study regimen should be permanently discontinued in Grade 2 events with high likelihood for morbidity and/or mortality – e.g., myocarditis, or other similar events even if they are not currently noted in the guidelines – when they do not rapidly improve to Grade <1 upon treatment with systemic steroids and following full taper
 
Note: There are some exceptions to permanent discontinuation of study drug for Grade 4 events (i.e., hyperthyroidism, hypothyroidism, Type 1 diabetes mellitus).
 | 
not currently noted in the guidelines – when these events are not responding to systemic steroids.
 
With long-term steroid and other immunosuppressive use, consider need for Pneumocystis jirovecii pneumonia (PJP, formerly known as Pneumocystis carinii pneumonia) prophylaxis, gastrointestinal protection, and glucose monitoring.
 
Discontinuation of study drug/study regimen is not mandated for Grade 3/Grade 4 inflammatory reactions attributed to local tumor response (e.g., inflammatory reaction at sites of metastatic disease and lymph nodes). Continuation of study drug/study regimen in this situation should be based upon a benefit-risk analysis for that patient.
 |

AE Adverse event; CTC Common Toxicity Criteria; CTCAE Common Terminology Criteria for Adverse Events; im/AE immune-mediated adverse event; IV intravenous; NCI National Cancer Institute; PO By mouth.

Pediatric Considerations

| Dose Modifications | Toxicity Management |
|--|--|

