| Permanently discontinue study drug/study regimen. | | Consider, as necessary, discussing with study physician. |
| Endocrinopathy (e.g., hyperthyroidism, hypothyroidism, Type 1 diabetes mellitus, hypophysitis, hypopituitarism, and adrenal insufficiency; exocrine event of amylase/lipase increased also included in this section) | Any Grade (depending on the type of endocrinopathy, refer to NCI CTCAE v4.03 for defining the CTC grade/severity) | For Any Grade: |
| | General Guidance | 
 Consider consulting an endocrinologist for endocrine events. Consider, as necessary, discussing with study physician. Monitor patients for signs and symptoms of endocrinopathies. Non-specific symptoms include headache, fatigue, behavior changes, changed mental status, vertigo, abdominal pain, unusual bowel habits, polydipsia, polyuria, hypotension, and weakness. Patients should be thoroughly evaluated to rule out any alternative etiology (e.g., disease progression including brain metastases, or infections). Depending on the suspected endocrinopathy, monitor and evaluate thyroid function tests: TSH, free T3 and free T4 and other relevant endocrine and related labs (e.g., blood glucose and ketone levels, HgA1c). For modest asymptomatic elevations in serum amylase and lipase, corticosteroid treatment is not indicated as long as there are no other signs or symptoms of pancreatic inflammation. If a patient experiences an AE that is thought to be possibly of autoimmune nature (e.g., thyroiditis, pancreatitis, hypophysitis, or diabetes insipidus), the investigator should send a blood sample for appropriate autoimmune antibody testing. |
| Grade 1 | No dose modifications. | For Grade 1 (including those with asymptomatic TSH elevation): |
| | | 
 Monitor patient with appropriate endocrine function tests. For suspected hypophysitis/hypopituitarism, consider consultation of an endocrinologist to guide assessment of early-morning ACTH, cortisol, TSH and free T4; also consider gonadotropins, sex hormones, and prolactin levels, as well as cosyntropin stimulation test (though it may not be useful in diagnosing early secondary adrenal insufficiency). If TSH < 0.5 × LLN, or TSH > 2 × ULN, or consistently out of range in 2 subsequent measurements, include free T4 at subsequent cycles as clinically indicated and consider consultation of an endocrinologist. |

| | | |
|---------------------|--|---|

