| Grade 3 or 4 | 
For Grade 3 or 4 endocrinopathy other than hypothyroidism and Type 1 diabetes mellitus, hold study drug/study regimen dose until endocrinopathy symptom(s) are controlled.
 
Study drug/study regimen can be resumed once event stabilizes and after completion of steroid taper.
 
Patients with endocrinopathies who may require prolonged or continued steroid replacement (e.g., adrenal insufficiency)
 | 
For Grade 3 or 4:
 
 Consult endocrinologist to guide evaluation of endocrine function and, as indicated by suspected endocrinopathy and as clinically indicated, consider pituitary scan. Hospitalization recommended. For all patients with abnormal endocrine work up, except those with isolated hypothyroidism or Type 1 DM, and as guided by an endocrinologist, promptly initiate empiric IV methylprednisolone 1 to 2 mg/kg/day or equivalent, as well as relevant hormone replacement (e.g., hydrocortisone, sex hormones). For adrenal crisis, severe dehydration, hypotension, or shock, immediately initiate IV corticosteroids with mineralocorticoid activity. |

| | |
|--|--|
| 
can be retreated with study drug/study regimen on the following conditions:
 
 The event stabilizes and is controlled. The patient is clinically stable as per investigator or treating physician's clinical judgement. Doses of prednisone are ≤ 10 mg/day or equivalent. | 
Isolated hypothyroidism may be treated with replacement therapy, without study drug/study regimen interruption, and without corticosteroids.
 
Isolated Type 1 diabetes mellitus may be treated with appropriate diabetic therapy, without study drug/study regimen interruption, and without corticosteroids.
 
Once patients on steroids are improving, gradually taper immunosuppressive steroids (as appropriate and with guidance of endocrinologist) over ≥ 28 days and consider prophylactic antibiotics, antifungals, and anti-PJP treatment (refer to current NCCN guidelines for treatment of cancer-related infections [Category 2B recommendation]).³
 |

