| Any Grade | Note: Dose modifications are not required for AEs not deemed to be related to study treatment (i.e., events due to underlying disease) or for laboratory abnormalities not deemed to be clinically significant. | Treat accordingly, as per institutional standard. |
| Grade 1 | No dose modifications. | Treat accordingly, as per institutional standard. |
| Grade 2 | Hold study drug/study regimen until resolution to ≤Grade 1 or baseline. | Treat accordingly, as per institutional standard. |
| Grade 3 | Hold study drug/study regimen until resolution to ≤Grade 1 or baseline. For AEs that downgrade to ≤Grade 2 within 7 days or resolve to ≤Grade 1 or baseline within 14 days, resume study drug/study regimen administration. Otherwise, discontinue study drug/study regimen. | Treat accordingly, as per institutional standard. |
| Grade 4 | Discontinue study drug/study regimen (Note: For Grade 4 labs, decision to discontinue should be based on accompanying clinical signs/symptoms, the Investigator's clinical judgment, and consultation with the Sponsor.) | Treat accordingly, as per institutional standard. |

Note: As applicable, for early phase studies, the following sentence may be added: "Any event greater than or equal to Grade 2, please discuss with Study Physician."
 AE Adverse event; CTCAE Common Terminology Criteria for Adverse Events; NCI National Cancer Institute.

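### Appendix III gives conflicting stop and resume instructions in two narrow cases: Grade 4 hypophysitis, hypopituitarism and adrenal insufficiency, and non-immune Grade 3 events that fall to Grade 2 within 7 days

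*Protocol*

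**What the plan says.** **Endocrine events.** In Appendix III, General Considerations, the Grade 4 line reads "Grade 4 Permanently discontinue study drug/study regimen". A note in the same table adds: "There are some exceptions to permanent discontinuation of study drug for Grade 4 events (i.e., hyperthyroidism, hypothyroidism, Type 1 diabetes mellitus". The Endocrinopathy section of the same appendix covers "hyperthyroidism, hypothyroidism, Type 1 diabetes mellitus, hypophysitis, hypopituitarism, and adrenal insufficiency". Its row for the two highest grades says: "For Grade 3 or 4 endocrinopathy other than hypothyroidism and Type 1 diabetes mellitus, hold study drug/study regimen dose until endocrinopathy symptom(s) are controlled", and then "Study drug/study regimen can be resumed once event stabilizes and after completion of steroid taper".

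**Non-immune events.** In the Non-Immune-Mediated Reactions table, the Grade 3 cell opens with "Hold study drug/study regimen until resolution to ≤Grade 1 or baseline" and continues "For AEs that downgrade to ≤Grade 2 within 7 days or resolve to ≤Grade 1 or baseline within 14 days, resume study drug/study regimen administration". If neither limit is met, the drug is to be discontinued. The Grade 2 row above carries the same hold instruction.

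**Rules that might settle a conflict.** Section 7.1.4 tells sites to apply the greatest hold or discontinuation when a patient has several adverse events whose recommendations differ. It also obliges centres to contact the coordinating group about severe immune-related events. Section 10.1 makes unacceptable toxicity, defined by reference to Section 7.0 and Appendix III, a ground for stopping treatment.

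**The concern.** Each event and grade should lead to one instruction. Here some lead to two, and the events are severe or life-threatening. A site could restart drug after a Grade 4 adrenal event in line with one table and thereby break the other. For a non-immune event sitting at Grade 2, giving the next infusion and omitting it each follow one sentence of the same cell.

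The first consequence is for patient safety. The second is for the data. SAP Section 4.3 lists dose interruptions, delivered dose, dose modifications and reasons off treatment as safety endpoints, and these are summarised in Tables 27–31 and 58. If the rule differs from site to site, those tables mix differences in toxicity with differences in how the appendix was read.

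**Working it through.** The plan states no figure to reproduce, so the check is mainly a comparison of text.

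**(a) The six named endocrinopathies at Grade 4**

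| Event | General Considerations | Endocrinopathy row, Grade 3 or 4 | Result |
|---|---|---|---|
| Hypothyroidism | excepted from the stop | left out of the hold; may be treated without interruption | agree |
| Type 1 diabetes | excepted from the stop | left out of the hold; may be treated without interruption | agree |
| Hyperthyroidism | excepted from the stop | hold, may resume | agree |
| Hypophysitis | permanent stop | hold, may resume | conflict |
| Hypopituitarism | permanent stop | hold, may resume | conflict |
| Adrenal insufficiency | permanent stop | hold, may resume | conflict |

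Six named events less three excepted leaves three in conflict. Three further observations support this reading:

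- In General Considerations the Grade 3 line defers to the event tables ("Please refer to guidelines below"). The Grade 4 line does not.
- General Considerations puts retreatment of patients on continuing steroid replacement under Grade 2 only. The Endocrinopathy section repeats it for Grade 3 or 4 and gives adrenal insufficiency as its example.
- The other nine immune-mediated sections (pneumonitis, diarrhea/colitis, hepatitis, nephritis, rash, neurotoxicity, peripheral neuromotor syndromes, myocarditis, myositis) all stop permanently at Grade 4. Endocrinopathy is the only one that departs from the general line.

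**(b) A non-immune Grade 3 event**

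| Course | Hold sentence | Resume/discontinue sentences | Result |
|---|---|---|---|
| Grade 1 or lower, or baseline, within 14 days | hold ends | resume | agree |
| Grade 2 within 7 days, not yet Grade 1 or baseline | hold continues | resume | conflict |
| Neither limit met | hold continues | discontinue | compatible: held, then stopped |

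Only the middle line conflicts. Infusions are given on Day 1 every 28 days (Section 7.1.1), and one that cannot be given is omitted until the next planned infusion (Section 7.1.4). The conflict therefore has effect when a planned infusion falls while the event is still at Grade 2.

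**Illustration of the effect on a SAP summary.** This uses the dose-intensity formula in SAP Section 7.5.3. Assume a patient reaches cycle 4 with the first and fourth durvalumab infusions given on schedule, 3 × 28 = 84 days apart. The denominator is (84 + 28)/7 = 16 weeks.

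- All four infusions given: 4 × 1500/16 = 375 mg/week; 375/375 = 100%.
- One intermediate infusion omitted: 3 × 1500/16 = 281.25 mg/week; 281.25/375 = 75%.

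One such decision moves this patient from the top category of Table 30 to the 60% to under 80% category. This shows how a single patient's entry changes. It does not estimate how often that happens.

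**The case against.** The strongest answer is that the appendix runs from general to specific, so the event row should be taken to prevail. General Considerations also contains other departures from the Grade 4 stop besides the three named conditions: asymptomatic amylase or lipase elevation, and reactions attributed to local tumour response. The named list is therefore not the whole set of exceptions. That stands, but none of those departures covers the three events, and no text says that the specific row wins. Extending the greatest-hold rule of Section 7.1.4 by analogy gives the other answer.

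A reader might infer that sites following the document exactly would be bound to treat the same patient in opposite ways. For the endocrine case the documents do not support that. The Endocrinopathy row permits resumption and does not require it, so a site that stops permanently breaches nothing. Section 7.1.4 also brings severe immune-related events to the coordinating group. This lessens the conflict, but the site that resumes still departs from the Grade 4 line.

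For the non-immune case, the 7- and 14-day limits could be read as deciding only whether the patient may continue at all, with dosing still waiting for the hold criterion. That reading is coherent but it is not written, and the literal instruction is to resume.

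Timing also limits the reach. The appendix is dated 1 November 2017. Randomization closed on June 29, 2017 (SAP Section 2.1), and treatment starts within 2 working days. Without delays, a fourth tremelimumab dose 84 days after the first falls in late September 2017. This version would then govern mainly patients remaining on durvalumab alone. Earlier versions of the appendix are not available, so whether they carried the same wording is unknown.

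**Conclusion.** Both conflicts are in the current text, and nothing in the protocol resolves them. Their scope is narrow: three named endocrinopathies at Grade 4, and treatment-related non-immune Grade 3 events still at Grade 2 when an infusion is due after reaching that grade within 7 days. The documents give no rates for these events, so the number of patients affected cannot be stated.

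Three wider readings are not supported:

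- **All Grade 4 endocrinopathies conflict.** The exception note removes the conflict for hyperthyroidism, hypothyroidism and Type 1 diabetes.
- **Protocol-violation counts in SAP Table 5 would be distorted.** SAP Section 7.3.3 reserves major violations for deviations so serious that the patient's data contribute little or nothing. Following one of two printed instructions would not plausibly qualify.
- **The trial's main result is at risk.** The intent-to-treat log-rank comparison of overall survival and its sample size do not depend on these rules.

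What remains is a matter of patient safety and of consistency in descriptive exposure, off-treatment and discontinuation tables. The conclusion rests on the literal wording and on there being no precedence rule outside the two documents.

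**What to change.** Reconcile the Grade 4 line and its exception note in General Considerations with the Grade 3 or 4 Endocrinopathy row. Reconcile the two sentences of the non-immune Grade 3 cell with each other and with the Grade 2 row. Each event and grade should then have one instruction. Add a sentence stating which table prevails when a general and an event-specific row differ for a single event, since Section 7.1.4 speaks only to several events. The clinical content is for the sponsor and drug supplier to decide; no threshold or rule is proposed here.

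The cost is a wording change in one appendix, by short amendment or administrative letter, with no additional patients or data.

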| | Grade 2 (symptomatic; medical intervention indicated; limiting instrumental ADL) | Hold study drug/study regimen dose until 
 Grade 2 resolution to Grade ≤1. If toxicity worsens, then treat as Grade 3 or Grade 4. If toxicity improves to Grade ≤1, then the decision to reinitiate study drug/study regimen will be based upon treating physician's clinical judgment and after completion of steroid taper. | For Grade 2 (mild to moderate new symptoms): 
 Monitor symptoms daily and consider hospitalization. Promptly start systemic steroids (e.g., prednisone 1 to 2 mg/kg/day PO or IV equivalent). Reimage as clinically indicated. If no improvement within 3 to 5 days, additional workup should be considered and prompt treatment with IV methylprednisolone 2 to 4 mg/kg/day started If still no improvement within 3 to 5 days despite IV methylprednisolone at 2 to 4 mg/kg/day, promptly start immunosuppressive therapy such as TNF inhibitors (e.g., infliximab at 5 mg/kg every 2 weeks). Caution: It is important to rule out sepsis and refer to infliximab label for general guidance before using infliximab. Once the patient is improving, gradually taper steroids over ≥28 days and consider prophylactic antibiotics, antifungals, or |

Dosing Modification and Toxicity Management - 1 November 2017 - Page 4 of 23

| | |
|---|---|
| 
anti-PIP treatment (refer to current NCCN guidelines for treatment of cancer-related infections [Category 2B recommendation])^a
 
 - Consider pulmonary and infectious disease consult. - Consider, as necessary, discussing with study physician. | |

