| Grade 1 (Diarrhea: stool frequency of <4 over baseline per day) (Colitis: asymptomatic; clinical or diagnostic observations only) | No dose modifications. | For Grade 1: 
 Monitor closely for worsening symptoms. Consider symptomatic treatment, including hydration, electrolyte replacement, dietary changes (e.g., American Dietetic Association colitis diet), and loperamide. Use probiotics as per treating physician's clinical judgment. |
| Grade 2 (Diarrhea: stool frequency of 4 to 6 over baseline per day) (Colitis: abdominal pain; mucus or blood in stool) | Hold study drug/study regimen until resolution to Grade ≤ 1 
 If toxicity worsens, then treat as Grade 3 or Grade 4. If toxicity improves to Grade ≤ 1, then study drug/study regimen can be resumed after completion of steroid taper. | For Grade 2: 
 Consider symptomatic treatment, including hydration, electrolyte replacement, dietary changes (e.g., American Dietetic Association colitis diet), and loperamide and/or budesonide. Promptly start prednisone 1 to 2 mg/kg/day PO or IV equivalent. If event is not responsive within 3 to 5 days or worsens despite prednisone at 1 to 2 mg/kg/day PO or IV equivalent, GI consult should be obtained for consideration of further workup, such as imaging and/or colonoscopy, to confirm colitis and rule out perforation, and prompt treatment with IV methylprednisolone 2 to 4 mg/kg/day started. If still no improvement within 3 to 5 days despite 2 to 4 mg/kg IV methylprednisolone, promptly start immunosuppressives such as infliximab at 5 mg/kg once every 2 weeks^a. Caution: it is important to rule out bowel perforation and refer to infliximab label for general guidance before using infliximab. Consider, as necessary, discussing with study physician if no resolution to Grade ≤ 1 in 3 to 4 days. Once the patient is improving, gradually taper steroids over ≥ 28 days and consider prophylactic antibiotics, antifungals, and anti-PJP treatment (refer to current NCCN guidelines for treatment of cancer-related infections [Category 2B recommendation]).^a |
| Grade 3 or 4 | Grade 3 Permanently discontinue study drug/study | For Grade 3 or 4: |

| | | | |
|---|---|---|--|

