| | | | 
 - Consult with nephrologist. - Monitor for signs and symptoms that may be related to changes in renal function (e.g., routine urinalysis, elevated serum BUN and creatinine, decreased creatinine clearance, electrolyte imbalance, decrease in urine output, or proteinuria). - Patients should be thoroughly evaluated to rule out any alternative etiology (e.g., disease progression or infections). - Steroids should be considered in the absence of clear alternative etiology even for low-grade events (Grade 2), in order to prevent potential progression to higher grade event. |

| Grade 1 (Serum creatinine > 1 to $1.5 \times$ baseline; $> ULN$ to $1.5 \times ULN$) | No dose modifications. | For Grade 1: |
|--|---|--|
| | | 
 - Monitor serum creatinine weekly and any accompanying symptoms. 
 • If creatinine returns to baseline, resume its regular monitoring per study protocol. • If creatinine worsens, depending on the severity, treat as Grade 2, 3, or 4. - Consider symptomatic treatment, including hydration, electrolyte replacement, and diuretics. |
| Grade 2 | Hold study drug/study regimen until resolution to Grade ≤ 1 or baseline. | For Grade 2: |
| | | 
 - Consider symptomatic treatment, including hydration, electrolyte replacement, and diuretics. |

| | | |
|--|---|---|

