| 
(serum creatinine >1.5 to 3.0 × baseline; >1.5 to 3.0 × ULN)
 | 
 • If toxicity worsens, then treat as Grade 3 or 4. • If toxicity improves to Grade ≤1 or baseline, then resume study drug/study regimen after completion of steroid taper. | 
 - Carefully monitor serum creatinine every 2 to 3 days and as clinically warranted. - Consult nephrologist and consider renal biopsy if clinically indicated. - If event is persistent (>3 to 5 days) or worsens, promptly start prednisone 1 to 2 mg/kg/day PO or IV equivalent. - If event is not responsive within 3 to 5 days or worsens despite prednisone at 1 to 2 mg/kg/day PO or IV equivalent, additional workup should be considered and prompt treatment with IV methylprednisolone at 2 to 4 mg/kg/day started. - Once the patient is improving, gradually taper steroids over ≥28 days and consider prophylactic antibiotics, antifungals, and anti-PJP treatment (refer to current NCCN guidelines for treatment of cancer-related infections [Category 2B recommendation]).^a - When event returns to baseline, resume study drug/study regimen and routine serum creatinine monitoring per study protocol. |
| 
Grade 3 or 4 (Grade 3: serum creatinine >3.0 × baseline; >3.0 to 6.0 × ULN; Grade 4: serum creatinine >6.0 × ULN)
 | 
Permanently discontinue study drug/study regimen.
 | 
For Grade 3 or 4:
 
 - Carefully monitor serum creatinine on daily basis. - Consult nephrologist and consider renal biopsy if clinically indicated. - Promptly start prednisone 1 to 2 mg/kg/day PO or IV equivalent. - If event is not responsive within 3 to 5 days or worsens despite prednisone at 1 to 2 mg/kg/day PO or IV equivalent, additional workup should be considered and prompt treatment with IV methylprednisolone 2 to 4 mg/kg/day started. - Once the patient is improving, gradually taper steroids over ≥28 days and consider prophylactic antibiotics, antifungals, and anti-PJP treatment (refer to current NCCN guidelines for treatment of cancer-related infections [Category 2B recommendation]).^a |
| 
Rash
 | 
Any Grade (refer to NCI CTCAE v 4.03 for definition of
 | 
General Guidance
 
 - Monitor for signs and symptoms of dermatitis (rash and pruritus). |

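### Appendix III, Grade 2 nephritis: one Toxicity Management bullet restarts study drug at return to baseline and omits the completed-taper condition that the same row requires

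*Protocol*

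**What the plan says.** Appendix III, Nephritis or renal dysfunction, Grade 2, gives restart instructions in two columns.

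- Dose Modifications: "If toxicity improves to Grade ≤1 or baseline, then resume study drug/study regimen after completion of steroid taper".
- Toxicity Management: prednisone 1 to 2 mg/kg/day if the event lasts more than 3 to 5 days or worsens; then "Once the patient is improving, gradually taper steroids over ≥28 days"; and, as the final bullet, "When event returns to baseline, resume study drug/study regimen and routine serum creatinine monitoring per study protocol".

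The General Considerations of the same appendix set the rule for Grade 2 events overall: "Study drug/study regimen can be resumed once event stabilizes to Grade ≤1 after completion of steroid taper".

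The Grade 1 nephritis row uses return to baseline only as a monitoring trigger: "Monitor serum creatinine weekly and any accompanying symptoms", and then "If creatinine returns to baseline, resume its regular monitoring per study protocol".

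Three sections of the protocol body bear on the matter. Section 7.1.1 sets a 28-day cycle. Section 7.1.4 omits a missed infusion until the next planned one, and has a tie-break in favour of the longest hold when a patient has several adverse events. Section 7.2.2 lists IV or oral corticosteroids as not permitted, with limited exceptions that include oral doses up to 10 mg prednisone equivalent.

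**The concern.** The final management bullet is a second restart instruction for the same event and grade, and it lacks the condition that the first one carries. It comes directly after the bullet that orders the taper. A site working down the management column could therefore start the taper, see creatinine return to baseline, and give the next infusion while the patient is still on systemic steroids. The dosing cell beside it says to wait.

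Two things are at stake. One is the safety of an individual patient re-exposed to a checkpoint inhibitor before immunosuppression has been withdrawn. The other is how the infusion is classified. SAP Section 7.5.2 and Table 26 sort patients by whether all administrations followed the protocol, and an infusion during the taper satisfies one sentence and breaks the other. Tables 27 to 30 (omissions, cumulative dose, dose intensity) would shift slightly as well. All of these are descriptive.

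**Working it through.** The plan states no figure to reproduce. The check is a comparison of texts followed by calendar arithmetic.

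**1. The restart texts side by side**

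| Source (Appendix III) | Recovery level | Completed taper required? |
|---|---|---|
| General Considerations, Grade 2 | Grade ≤1 | Yes |
| Nephritis Grade 2, Dose Modifications | Grade ≤1 or baseline | Yes |
| Nephritis Grade 2, Toxicity Management | Baseline | Not stated |

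The recovery levels are compatible: a patient at baseline meets all three. Only the last column differs.

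**2. Which text is the outlier**

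The appendix covers 10 specific immune-mediated reactions. At Grade 2, 8 of the 10 Dose Modifications texts require a completed taper: pneumonitis ("clinical judgment and after completion of steroid taper"), colitis ("then study drug/study regimen can be resumed after completion of steroid taper"), hepatitis, nephritis, rash, endocrinopathy, neurotoxicity and myocarditis. The peripheral neuromotor and myositis rows are silent. As far as the table can be read in the available copy, nephritis is the only one of the 10 whose Toxicity Management text orders drug to be resumed. So the bullet, not the dosing cell, is out of line.

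**3. Can an infusion fall inside the taper?**

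Inputs: planned infusions on days 0, 28, 56, 84 (Section 7.1.1); taper length T ≥ 28 days (the nephritis row). Let the taper start s days after the last planned date, s = 0 to 27. A planned date d lies strictly inside the taper if s < d < s + T.

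- T = 28: day 28 is inside when 28 < s + 28, that is s > 0. This holds for 27 of 28 start days; the exception is s = 0.
- T = 42 (assumed): day 28 is always inside; day 56 is also inside when s > 14, which is 13 start days. One date for 15 start days, two for 13.
- T = 56 (assumed): day 28 is always inside; day 56 is also inside when s > 0. Two dates for 27 start days, one for s = 0.

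Let creatinine reach baseline on day b, with s = 1 to 27 and b between s and s + T. The bullet alone doses at the first planned date on or after b. The dosing cell doses at the first planned date on or after max(b, s + T). For T = 28, s + T lies between 29 and 55, so the dosing cell gives day 56. The bullet gives day 28 if b ≤ 28 and day 56 otherwise. The difference is 1 infusion if b ≤ 28 and 0 if not. For T = 42 or 56 it is 0, 1 or 2.

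**4. How much Section 7.2.2 closes the gap**

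At the 75 kg average weight used in Section 3.3, the starting dose is 1 × 75 = 75 mg to 2 × 75 = 150 mg a day, well above 10 mg. As an illustration only, assume a straight-line taper to zero over 28 days. The dose is then 10 mg or less for the last 28 × 10/75 = 3.7 days, or 28 × 10/150 = 1.9 days. Day 28 falls in that closing window for s = 1, 2 or 3 (3 of 28 start days), or for s = 1 only (1 of 28). A taper that lingers at low doses would widen the window. So 7.2.2, if followed, removes most of the overlap but not the low-dose end.

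**5. Reach**

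The guideline is dated 1 November 2017 and accrual closed on 29 June 2017 (SAP Section 2.1), 125 days earlier. The protocol copy carries an administrative update of 24 January 2018, 209 days after closure, or 209/30.4375 = 6.9 months. That equals the median survival the design assumes for the experimental arm (Section 13.3).

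**The case against.** The strongest reply is that this is an incomplete summary bullet rather than a wrong rule. The column that governs dosing states the condition in full, the general Grade 2 rule repeats it, and the bullet is the last step of a sequence that has just ordered the taper. It nowhere says that drug may restart during the taper. No text in the protocol positively supports doing so. This largely stands. A reader might infer that the protocol authorises re-dosing on tapering steroids; taken as a whole, it does not.

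A reader might also infer that Section 7.2.2 leaves the question open because it accepts immunosuppressives for product-related adverse events. That allowance sits in the bullet on other agents such as methotrexate, azathioprine and TNF-α blockers. Systemic corticosteroids have their own, narrower bullet, and it points towards waiting at least until the dose is 10 mg or less. It does not reach the low-dose end of the taper, where the dosing cell still says to wait.

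The Section 7.1.4 tie-break has the right spirit but is worded for several adverse events, not for two instructions about one.

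A further tempting reading is that the two cells set conflicting recovery thresholds. They do not: the bullet is the stricter of the two on recovery.

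Finally, the calendar result shows only that overlap is possible. It does not say how often Grade 2 nephritis is treated with steroids, how soon creatinine recovers, or how often a site would overlook the adjacent cell. The documents give none of these. What remains is one safety instruction that, followed literally and alone, leads to the wrong action.

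**Conclusion.** The inconsistency is real and minor. One bullet omits a condition that its own row and the general rule require, and the intended rule is to wait for the taper to finish.

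The difference is at most one infusion per affected patient with a 28-day taper, and 0 to 2 with assumed tapers of 42 or 56 days. These are conditional figures, since time to baseline is not given. Patients never given steroids have no taper and no conflict. Because this guideline version postdates accrual closure, it concerns mainly the patients still on durvalumab, probably few. Whether earlier versions carried the same bullet cannot be seen.

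A reader might infer a consequence for the trial's conclusions. The documents do not support that: the overall survival analysis, power and sample size do not depend on this rule.

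**What to change.** Reword the final Grade 2 nephritis bullet along these lines: *at return to baseline, go back to routine creatinine monitoring; restart study drug only as stated under Dose Modifications, after any steroid taper is complete.* Alternatively, delete the restart clause so that restart is stated only under Dose Modifications, as in the other nine reactions. Either choice keeps baseline as the monitoring trigger, consistent with the Grade 1 row.

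The cost is one sentence, with no new data, visits or procedures. The appendix reads as a generic guideline with its own version date, so if the template cannot be edited, a trial-specific clarification to sites is enough.
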